## Abbreviations and Terms

Abbreviation	Full text
AE	Adverse event
AG-920	Articaine sterile topical ophthalmic solution
BCVA	Best corrected visual acuity
BOCF	Baseline observation carried forward
CFR	Code of Federal Regulations
COVID-19	Coronavirus Disease 2019
CRO	Contract Research Organization
EDC	Electronic Data Capture
ETDRS	Early Treatment of Diabetic Retinopathy Study
FDA	Food and Drug Administration
GCP	Good Clinical Practices
GLP	Good Laboratory Practices
GMP	Good Manufacturing Practices
HCl	Hydrochloride
ICH	International Conference on Harmonisation
ICF	Informed Consent Form
IEC	Independent Ethics Committee
IMP	Investigational Medical Product
IOP	Intraocular pressure
IRB	Institutional Review Board
ITT	Intent-to-Treat
LOCF	Last Observation Carried Forward
logMAR	Logarithmic Minimum Angle of Resolution
MedDRA	Medical Dictionary for Regulatory Activities
NSAID	Non-steroidal anti-inflammatory drug
OD	Oculus dexter (Right eye)
OTC	Over the Counter
OS	Oculus sinister (Left eye)
PP	Per protocol
PPE	Personal protective equipment
PT	Preferred Term
SAE	Serious adverse event
SAP	Statistical Analysis Plan
SOC	System/Order/Class
SOP	Standard Operating Procedures
TEAE	Treatment emergent adverse event
US	United States
VA	Visual acuity

## Summary

Study Number	AG-920-CS304	
Clinical Phase:	Phase 3	
Type of study	Efficacy and Safety	
Name of Investigational product:	Articaine Sterile Topical Ophthalmic Solution (AG-920)	
Name of Comparator product	0.5% Proparacaine Hydrochloride	
Duration of treatment per subject	1 day	
Objectives and Endpoints:	Primary Objective	Primary Endpoints
	To evaluate anesthetic efficacy of AG-920	The proportion of subjects in which an eye exam was able to be performed
	Secondary Objective	Secondary Endpoints
	To evaluate the safety and tolerability of AG-920	Incidence of AEs, TEAEs, SAEs, withdrawals due to TEAEs
Subject Population:	Healthy pediatric volunteers Exclusion criteria may be found in Section 4.2.	
Design:	Randomized, active-controlled, single-masked, parallel-group.	
Visit Schedule:	Study visits will consist of a Screening Visit, a dosing and eye exam visit, and a follow-up phone call	
Number of Investigational Sites:	1-3 US sites	
Estimated Total Sample Size:	Enroll up to 70 subjects to result in 60 evaluable subjects; ~30 per treatment group	
Plan for Data Analysis:	The sample size is as directed by the U.S. FDA for a Pediatric Study Plan.	
Investigational/Comparator Product(s), Dose and Mode of Administration	Subjects will receive a single dose (two drops) of IMP in one (study) eye. The IMP will be randomized as either AG-920 or Proparacaine HCl Ophthalmic Solution. The study eye will be randomized as either right eye (OD) or left eye (OS). The single dose will be administered by the clinic staff.	

## 1 INTRODUCTION

American Genomics is evaluating the formulation of articaine, an approved local anesthetic, for topical ocular use to provide local anesthesia. The Sponsor intends to develop Articaine Sterile Topical Ophthalmic Solution (AG-920) for topical ocular use to induce local anesthesia. The systemic exposure to articaine after topical ocular instillation is not expected to be greater than that with oral (dental) use of the marketed product, Septocaine® ([Package Insert](#)).

Injections of pharmacologic agents into the vitreous cavity for the purpose of treating various disorders of the retina as well as intraocular inflammatory disease have become the mainstream. In almost all cases, these injections are made through the pars plana. An injection into the eye in this location, with the needle oriented properly, will be posterior to the human lens or an intraocular implant, but anterior to the retina, thereby avoiding damage to these important structures. The pars plana is a zone that rings the eye extending from 3.0 mm to 5.5 mm from the edge of the cornea (Figure 1).

**Figure 1: Human Ocular Structure (coronal view)**

While topical agents such as Proparacaine achieve excellent anesthesia on the external surface of the eye, they do not numb the internal aspect of the pars plana, which is extremely sensitive. Currently, physicians fall into one of two methodologies: either injecting lidocaine under the conjunctiva first and then executing a second injection through the pars plana, or by using topical lidocaine gel and then performing the intravitreal injection. Patients often report moderate to severe discomfort with each of these approaches. The purpose of the AG-920 topical drop would be to allow a technician to apply the topical solution to the eye, allow the articaine to penetrate the pars plana sufficiently to permit the intravitreal injection without undue discomfort. Articaine was selected for this procedure based upon its clinical use in dental procedures, which suggest it penetrates soft tissue and bone.

### ***1.1 Findings from nonclinical and clinical studies***

Detailed information on nonclinical and clinical studies with articaine including AG-920 is provided in the [Investigator's Brochure \(2022\)](#).

### 1.2 *Potential Risks and benefits to human subjects*

Minimal risks are expected with AG-920. Based upon clinical trials conducted to date, expected risks for subjects may include temporary, mild conjunctival/ocular hyperemia, eye pain, instillation site reaction (stinging/burning), and conjunctival hemorrhage upon instillation of the investigational medicinal product (IMP). For any additional information on AG-920 use, please refer to the [Investigator's Brochure](#).

Minimal risks are expected with the comparator, Proparacaine HCl ophthalmic solution. Occasional temporary stinging, burning and conjunctival redness may occur with the use of Proparacaine. A rare, severe, immediate-type, apparently hyperallergic corneal reaction (characterized by acute, intense and diffuse epithelial keratitis, a gray, ground glass appearance, sloughing of large areas of necrotic epithelium, corneal filaments and, sometimes, iritis with descemetitis) has been reported. Allergic contact dermatitis from Proparacaine with drying and fissuring of the fingertips has also been reported. For any additional information on Proparacaine use, please refer to the [Package Insert](#).

As this study is to be conducted in healthy pediatric subjects, there is no anticipated benefit other than the possibility that a subject's participation in the present study may help others in the future to have more options for local anesthesia before ophthalmic procedures.

Any new, unexpected adverse events (AEs) present among subjects in this clinical trial will be communicated to Investigators and to ethics committees or Institutional Review Board (IRBs) in accordance with local regulations.

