**Secondary Objectives**

To evaluate the safety and tolerability of AG-920

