### 9.2 Sample Size Considerations

The sample size of approximately 70 subjects to be randomized in a 1:1 allocation ratio for AG-920 and reference groups is as directed by the U.S. FDA for a Pediatric Study Plan, rather than being estimated based on a pre-defined non-inferiority margin commonly used for the trial design of therapeutical equivalence. The Sponsor plans to enroll up to 70 subjects in order to obtain at least 60 evaluable subjects.

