#### Adverse Events

Adverse events will be coded for preferred terminologies using Medical Dictionary for Regulatory Activities (MedDRA). AEs will be grouped into pre-treatment AEs, treatment-emergent AEs, and post-treatment AEs and will be reported separately, based upon the start date and time of the events compared to the start date and time of the treatment.

Adverse events will be defined as pre-treatment AEs if they occur prior to the treatment start date and time; as treatment-emergent AEs if they occur on or after the treatment start date and time and before the next day; and as post-treatment AEs if they occur after the treatment date.

Frequency of treatment-emergent AEs will be calculated for each body system, by preferred terminology, by treatment group, for number of subjects and percentage reporting the event.

The severity of the adverse events and the relationship to the investigational product will be summarized for each body system and preferred terminology by treatment group. Withdrawals due to adverse events will be summarized for each body system and preferred terminology by treatment group and will be listed with demographic variables for individual subjects.

Serious adverse events (SAE) (including deaths) will be listed for individual events.

Narratives will be provided for all deaths, non-fatal serious adverse events, and subjects withdrawn due to adverse events.

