## 5.3 Adverse Events

An overall summary of AEs reported in this study will be provided in [Table 4.1.1](#) for study participants and in [Table 4.1.2](#) for the safety population. The incidences of subjects reporting pre-treatment AEs will be reported in [Table 4.2.1](#) for the pre-randomization period and in [Table 4.2.2](#) for the treatment-emergent AEs by treatment. Those treatment-emergent AEs by preferred terminology that are reported by more than 5% of subjects in any treatment will be tabulated in [Table 4.2.3](#).

Incidences of subjects reporting treatment-emergent AEs (TEAEs) will also be tabulated by treatment for the TEAEs associated with the study eye in [Table 4.2.5](#) and for the TEAEs associated with fellow eye in [Table 4.2.6](#).

Incidences of subjects reporting treatment-emergent AEs will also be tabulated by onset time (on-dosing day vs. post-dosing day) in [Table 4.3.1](#) for all TEAEs, and in [Table 4.3.2](#) for the TEAEs associated with the study eye, and in [Table 4.3.3](#) for the TEAEs associated with the fellow eye.

The severity of the treatment-emergent AEs and the relationship to the investigational product will be summarized in [Table 4.4.1](#).

Treatment-emergent AEs associated with early terminations and serious AEs will be summarized by preferred term, respectively, in [Table 4.4.2](#) and [Table 4.4.3](#) for all TEAEs, in [Table 4.4.4](#) and [Table 4.4.5](#) for the TEAEs associated with the study eye, and in [Table 4.4.6](#) and [Table 4.4.7](#) for the TEAEs associated with the fellow eye.

Details of AEs associated with both study and fellow eyes will be listed for each subject ([Listing 7](#))

Details of AEs associated with early terminations will be listed for each subject ([Listing 8](#)). SAEs, including deaths, will be listed for each event ([Listing 9](#)).

Narratives will be presented for all deaths, non-fatal serious adverse events, and subjects withdrawn due to adverse events.

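### No grouped count of instillation discomfort is prespecified, so no identified table gives the number of children per arm who had it, and the planned term-by-term comparison loses power if reports split over several terms

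*Protocol*

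**What the plan says.** The secondary objective in Protocol Section 2 is "To evaluate the safety and tolerability of AG-920". Its endpoint is the incidence of AEs, TEAEs, SAEs and withdrawals due to TEAEs.

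Protocol Section 1.2 names the expected local reactions. For AG-920, "expected risks for subjects may include temporary, mild conjunctival/ocular hyperemia, eye pain, instillation site reaction (stinging/burning), and conjunctival hemorrhage upon instillation". For the comparator, "Occasional temporary stinging, burning and conjunctival redness may occur with the use of Proparacaine". Sections 6.3 and 6.4.2 repeat the warning about stinging or burning.

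On counting, SAP Section 2.9.3 states: "Frequency of treatment-emergent AEs will be calculated for each body system, by preferred terminology, by treatment group". Protocol Section 9.4.8 adds a Fisher's exact test for each organ class and preferred term, and separate ocular and non-ocular summaries. SAP Section 5.3 defines Table 4.2.3: "Those treatment-emergent AEs by preferred terminology that are reported by more than 5% of subjects in any treatment will be tabulated".

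The SAP also plans:
- an overall AE summary (Tables 4.1.1 and 4.1.2);
- all TEAEs by preferred term without a cut (Table 4.2.2);
- study-eye and fellow-eye TEAEs (Tables 4.2.5 and 4.2.6);
- TEAEs by severity and relationship (Table 4.4.1);
- TEAEs associated with discontinuation (Table 4.4.2).

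Neither document defines a grouped discomfort event. The table shells are not part of the documents.

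**The concern.** For a treatment of two drops, discomfort on instillation is the tolerability event that the sponsor already expects. A reader will want one figure: how many children in each arm had it, and the difference. The plan produces rows for single terms, and totals that mix discomfort with every other event. Neither gives that figure.

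Two features make the split more than cosmetic. First, the protocol's own vocabulary differs by drug: eye pain and instillation site reaction for AG-920, stinging and burning for proparacaine. Second, Protocol Section 3.5 masks only the child and the parent or guardian, so the site staff who record the events know the treatment. The same reaction could be recorded under different terms in the two arms. The documents do not show that this will happen, but nothing in the plan guards against it.

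At stake are the clarity of the tolerability result and the chance of detecting a real difference in discomfort between the two drops.

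**Working it through.** The documents give no reaction rate, no coding rule for these words and no power figure for AE comparisons, so there is no stated figure to reproduce. Rates and the even split below are assumptions.

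**Inputs**
- Arm size: "The sample size of approximately 70 subjects to be randomized in a 1:1 allocation ratio for AG-920 and reference groups" (Protocol 9.2), so 70/2 = 35. With 60 evaluable, 60/2 = 30.
- Cut: strictly more than 5% in either arm, for each preferred term (SAP 5.3).
- Number of discomfort terms, k: two on the plain reading of Section 1.2 for AG-920; three or four only if stinging and burning are coded apart from instillation site reaction.

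**1. What the cut means in children.** 1/35 = 2.9% and 1/30 = 3.3% are not shown. 2/35 = 5.7% and 2/30 = 6.7% are shown. A term is left out only if each arm has at most one child with it.

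**2. Largest discomfort rate in one arm that can stay out of Table 4.2.3.** With one child per term this is k/n.

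| k | n = 35 | n = 30 |
|---|---|---|
| 2 | 2/35 = 5.7% | 2/30 = 6.7% |
| 3 | 3/35 = 8.6% | 3/30 = 10.0% |
| 4 | 4/35 = 11.4% | 4/30 = 13.3% |

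**3. How often this would happen.** Assume a true rate R = 10%, one term per affected child and an even split. The probability that exactly j children are affected, each under a different term, is C(k,j) × n!/(n−j)! × (R/k)^j × (1−R)^(n−j). Summing over j ≥ 2 gives the chance that the group exceeds 5% while none of its terms does, on that arm's counts.
- k = 2: 9.2% (n = 35), 11.4% (n = 30).
- k = 4: 24.1%, 27.6%.
- k = 4 and all four children affected (j = 4): 1.9%, 1.7%.

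The filter looks at either arm. If the other arm has the same rate, multiply by the chance that it too shows no term (the same sum over j ≥ 0).
- k = 2: 0.0919 × 0.2143 = 2.0% (n = 35); 0.1138 × 0.2975 = 3.4% (n = 30).
- k = 4: 0.2409 × 0.3633 = 8.8%; 0.2759 × 0.4596 = 12.7%.

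**4. Loss in the between-arm comparison.** Power of Fisher's exact test, two-sided 0.05, summed over both binomial distributions, with an even split over two terms:

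| True discomfort | Event compared | n = 35 | n = 30 |
|---|---|---|---|
| 40% v 10% | grouped | 78% | 71% |
| 20% v 5% | one given term of two | 33% | 24% |
| 30% v 10% | grouped | 46% | 37% |
| 15% v 5% | one given term of two | 14% | 9% |

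For 40% v 10%, the chance that at least one of the two terms is significant, without multiplicity adjustment, is 57% or 44% (simulation, 200,000 draws). If every report codes to one term, the grouped and single-term figures coincide and nothing is lost.

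**5. Why the rows cannot be added.** Suppose two term rows each show 3 of 35. The number of children with discomfort is then between 3 (all overlap) and 6 (none overlap), that is, between 3/35 = 8.6% and 6/35 = 17.1%. The table alone does not say which.

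**The case against.** The strongest reply is that nothing is concealed. Table 4.2.3 is an extract. Table 4.2.2 lists every preferred term without a cut, Table 4.2.5 covers the study eye, and Listing 7 gives the events child by child. In arms of 30 to 35, single-child rows are easy to see. This stands for visibility. It does not supply the count: the term rows cannot be added, and a figure assembled from the listing afterwards would rest on a grouping chosen with the data in view, in a trial where the site knows the assignments.

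A reader might infer that no planned table answers the tolerability objective, or that events are counted only by preferred term and organ class. The documents do not support either. The endpoint attached to that objective is overall AE and TEAE incidence, and the overall, study-eye, ocular and non-ocular, severity and relationship summaries address it. With the shells unavailable, it also cannot be shown that no table contains such a row, only that no title or text identifies one.

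A reader might also infer that a discomfort rate of 11% could readily vanish from the common-event table. That needs four terms with one child each. Section 1.2 clearly gives two terms for AG-920, with stinging and burning in parentheses as descriptions of one reaction, and MedDRA coding exists to bring varied wording together. On a true 10% rate, four one-child terms occur in under 2% of arms.

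Finally, no document claims power for AE comparisons, and the sample size was set by the regulator's pediatric plan. That is correct, so the power figures measure what splitting costs, not a broken promise. Nor do they show that discomfort would be missed from the tables: at 40% some term would almost always exceed 5%.

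**Conclusion.** The point holds as a gap in summarization. The plan prespecifies no grouped instillation-discomfort count, and no table identified by title or text gives the number of affected children by arm.

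The effect on Table 4.2.3 is modest: at most 5.7% to 6.7% discomfort left out with two terms, and 11.4% to 13.3% only in the unlikely four-term case. Omission is rarer still if both arms have similar rates. The effect on the comparison is larger: for 40% versus 10% over two terms, power falls from 78% or 71% to 33% or 24% for a given term, or to 57% or 44% for either term without adjustment.

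These sizes rest on assumed rates, an even split and one term per child. How reports will code is not in the documents, and the loss is zero if they all code to one term. No planned result is invalidated and the stated endpoint is still reported. The change is worth making because it is cheap and needs no new data.

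**What to change.** In SAP Sections 2.9.3 and 5.3, before any data review:

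1. List the preferred terms that form an instillation-discomfort group (eye pain, stinging, burning, instillation site reaction and synonyms) and, separately, an ocular-redness group (conjunctival or ocular hyperemia, redness).
2. Count each child once per group, in the study eye, by arm, with the between-arm difference and its 95% CI.
3. Apply the 5% rule of Table 4.2.3 to these groups as well as to single preferred terms.
4. Label the result a supportive tolerability summary, reported beside the stated AE-incidence endpoint and not in its place.

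The cost is a short term list and one extra table. The displayed reaction rate may be higher, and so less favorable, than any single-term row would suggest.

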### 1.3 *Design justification*

#### **Route of administration, dosage, dosage regimen, and treatment period(s)**

The dose selected for this study is based on clinical experience with this molecule by another route (dental) or from outside the United States, and preclinical safety studies. The positive-control design is as discussed with the U.S. FDA for ethically and scientifically appropriate investigation in the pediatric population. For more details, please refer to the [Investigator's Brochure](#).

The selected dose of the investigational medicinal product AG-920 is 8% Articaine Sterile Topical Ophthalmic Solution which contains 80 mg/mL of Articaine Hydrochloride (HCl).

The intended route of administration for AG-920 (testing treatment) and Proparacaine HCl Ophthalmic Solution (active-control or reference treatment) is topical ocular in this study. Each dose of AG-920 or Proparacaine HCl will consist of two drops 30 seconds apart in the study eye.

This study consists of a single treatment and subjects will be randomized 1:1 to AG-920 or Proparacaine HCl Ophthalmic Solution.

## 2 OBJECTIVES AND ENDPOINTS

#### **Primary Objective**

To evaluate anesthetic efficacy of AG-920

#### **Primary Endpoints**

The proportion of subjects in which an eye exam was able to be performed

**Secondary Objectives**

To evaluate the safety and tolerability of AG-920

**Secondary Endpoints**

Incidence of AEs, TEAEs, SAEs, withdrawals due to TEAEs

**3 STUDY DESIGN**

Randomized, Active-Controlled, single-masked, parallel.

**3.1 Description and schedule of visits and procedures**

This is a Phase 3, randomized, active-controlled, single-masked, parallel-group design study in healthy pediatric subjects performed in the US. It is designed to evaluate the safety and anesthetic efficacy of one dose of Articaine Sterile Topical Ophthalmic Solution (AG-920) compared to Proparacaine HCl Ophthalmic Solution (Proparacaine). In this study, parent/legal guardians will provide informed consent (and where applicable, subjects will provide assent). Subjects who fulfill all the inclusion criteria and none of the exclusion criteria will be randomized in a 1:1 ratio to receive a single dose of AG-920 or Proparacaine into one (study) eye.

Each dose of AG-920 or Proparacaine HCl will consist of two drops 30 seconds apart in the study eye. Two to 4 minutes after the completion of dosing, subjects will undergo an eye exam, and the ability to conduct that eye exam will be documented. IMP dosing will be performed by the study staff.

A schedule of assessments, including allowable visit windows, is displayed in Table 1.

**Table 1: Schedule of Visits and Procedures**

	Visit 1	Visit 2			Follow-Up
	Screening	Screening & Baseline			Phone call
	Day -2 - 0/1 Pre-dose	Day 1			Day 2-5
Procedures		Dose		2 -4 min post last drop	15-60 min post eye exam
		0 sec	30 sec		
Written Assent/Informed Consent	X				
Inclusion/Exclusion Criteria 	X	X 			
Demographics, Systemic and Ocular Medical History	X				
Concomitant Medication Query	X	-----X-----			X
Visual Acuity 	X 				X 
External Eye Exam	X				X
Biomicroscopy 					X 
Randomization		X 			
IMP Administration 		X	X 		
Eye Exam Procedure				X	
Adverse Event Assessment		-----X-----			X

IMP = investigational medicinal product

 Screening may occur on the same day as Visit 2 or up to 3 days previously. If on separate days, inclusion/exclusion criteria should be re-evaluated prior to dosing subject to ensure subject still qualifies.

 If Visit 1 and 2 are not performed on the same day, these assessments must be performed prior to dosing at 0 seconds.

 Age appropriate optotype (if capable) with clinically appropriate test (either Teller acuity charts, Allen pictures, HOTV letters, or Snellen acuity, per standard of care), or reaction to light (if not).

 Biomicroscopy only performed if necessary for a suspected AE

 One dose is 2 drops. First drop administered at 0 seconds and the second drop administered at 30 seconds (2 drops 30 seconds apart).

### 3.2 Measures taken to minimize/avoid bias

The subject and parent/legal guardian will be masked to treatment assignment throughout the conduct of the study by use of an “overwrap” label of the marketed product (Proparacaine). A randomization code will be generated by an independent statistician and will assign study drug (AG-920 or Proparacaine) to be received as well as the study eye to be used for each subject.

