**Figure 2: Investigational Medicinal Product**

	INVESTIGATIONAL PRODUCT	
PRODUCT NAME	Articaine Sterile Topical Ophthalmic Solution (AG-920)	Proparacaine HCl Ophthalmic Solution, 0.5%
ACTIVE INGREDIENT	Articaine Hydrochloride	Proparacaine HCl
INACTIVE INGREDIENTS	[REDACTED]	Glycerin Purified water Benzalkonium chloride 0.01%
UNIT DOSE	[REDACTED]	15 mL dropper bottle
ROUTE OF ADMINISTRATION	Topical ocular	Topical ocular
DOSING REGIMEN	2 drops 30 seconds apart from a single vial into study eye	2 drops 30 seconds apart from a single bottle into study eye
STORAGE REQUIREMENTS	[REDACTED]	Store bottles under refrigeration at 2° to 8°C (36° to 46°F)

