#### 3.3.1 IMP Packaging and labeling

Investigational Medicinal Product (IMP) will be packaged with an investigational label. Marketed Proparacaine HCl Ophthalmic Solution will be “overwrapped” with an investigational label.

The container-closure system to be used for the AG-920 in this clinical study [REDACTED] vial. [REDACTED]

Each foil pouch will be labeled with an investigational label with the following minimal

information: the study number, kit number, and storage statement, including a statement “Caution – New Drug – Limited by Federal (US) Law to Investigational Use” or equivalent. Each foil pouch will be individually placed into a single-unit carton and a similar investigational label will be applied to the carton.

The comparator product, 0.5% Proparacaine Hydrochloride [REDACTED], is packaged [REDACTED]. The bottles will be stored in a kit comprised of an individually labeled carton containing 1 bottle. [REDACTED]

[REDACTED] Each kit will be labeled with an investigational label with the following minimal information: the study number, kit number, and storage statement, including a statement “Caution – New Drug – Limited by Federal (US) Law to Investigational Use” or equivalent.

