### 3.5 Randomization and procedure for breaking the code

A randomization code for allocating the treatments and study eye will be prepared by an independent biostatistician, who is not involved in the day-to-day conduct of the study. Subjects

will be randomized in a 1:1 ratio to receive AG-920 or Proparacaine HCl Ophthalmic Solution. The site will have a randomization list that will assign each subject to treatment and study eye.

The study is single masked. Treatment assignments will be masked to the subjects and their parent/legal guardian only so there is no reason to break the code.

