##### 6.4.2 IMP Treatment

- Once qualification is confirmed, subject will be randomized.
  - Subject will be randomly assigned to receive a single dose of either AG-920 or Proparacaine HCl Ophthalmic Solution
  - Subject will be randomly assigned to receive the IMP dose into one eye (OD or OS) only (study eye)
  - Subjects and parent/legal guardian should be reminded that instillation of study drug, like other topical anesthetic drops, may cause a mild stinging or burning sensation upon instillation.
- Retrieve IMP kit number assigned and confirm study eye.
- For AG-920:
  - [REDACTED]
  - Administer 1 drop of IMP to the study eye
    - Wait 30 seconds
    - Administer a second drop of IMP to the same study eye from the same vial

- [REDACTED]
- For Proparacaine:
  - Remove dropper bottle from kit (carton)
  - Open bottle top
  - Administer 1 drop of IMP to the study eye
  - Wait 30 seconds
  - Administer a second drop of IMP to the same study eye from the same vial
  - Recap bottle and retain used bottle in the carton (kit) for accountability
- Assess for adverse events

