### 6.4.4 Follow-Up Phone Call (Day 2-5)

Subjects/parent/legal guardian will receive a phone call from site staff between Days 2-5, which is 1-4 days (24-96 hours post-dose) following treatment with IMP. Subjects/parents/legal guardians will be asked about

- AEs
- Changes to concomitant medications

If there are any ongoing adverse events, the subject will be instructed to return to the investigator's office for appropriate evaluation. If there are no ongoing adverse events, the subject will be considered completed.

Subjects and parents/legal guardians will be thanked for their participation and released to follow their normal standard of care.

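### The only family-masking measure described is an overwrap label on Proparacaine, yet the arms are dosed from visibly different containers, so masking of families throughout the study is not secured

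*Protocol*

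**What the plan says.** Protocol Section 3.2 makes the masking claim: "The subject and parent/legal guardian will be masked to treatment assignment throughout the conduct of the study by use of an". The rest of that sentence names the means, which is an overwrap label on the comparator. Section 3.3.1 and SAP Section 2.4 repeat the overwrap and, in their readable text, add no other measure.

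Section 3.5 limits the mask to families: "Treatment assignments will be masked to the subjects and their parent/legal guardian only so there is no reason to break the code". SAP Section 2.4 gives the same scope and adds that the study medication itself is masked to them.

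The products differ in presentation. Figure 2 gives the AG-920 regimen as "2 drops 30 seconds apart from a single vial into study eye", and Section 3.3.1 says of its packaging: "Each foil pouch will be individually placed into a single-unit carton". The Proparacaine unit in Figure 2 is a "15 mL dropper bottle", supplied one to a labeled carton. In Section 6.4.2 the Proparacaine sequence is to take the bottle from the carton, open it, give one drop, wait 30 seconds, give the second drop, and then "Recap bottle and retain used bottle in the carton (kit) for accountability".

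Section 6.4.4 describes the Day 2-5 call. "Subjects/parents/legal guardians will be asked about" adverse events and changes in medication.

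**The concern.** A label can cover a brand name. It cannot disguise whether the drops come from a pouched vial or from a 15 mL bottle that is opened and recapped. If the family sees the container and connects it with one of the two products, the mask is gone, and the label has not prevented that.

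Families are the only people from whom treatment is said to be hidden during conduct, so this mask is the plan's one stated protection against expectation affecting what they report. The outcome concerned is the secondary endpoint, the incidence of adverse events. Section 1.2 lists stinging, burning and eye pain among the expected risks. These are subjective complaints that a child voices or a parent relays. A family that believes it received the new product might report more of them, and one that believes it received the usual drop might report fewer.

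**Working it through.** The plan states no figure on masking, so the check sets the passages side by side.

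**1. Containers and handling**

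| | AG-920 | Proparacaine |
|---|---|---|
| Container at dosing (Figure 2) | Single vial | 15 mL dropper bottle |
| Outer packaging (3.3.1) | Foil pouch in a single-unit carton | Carton holding one bottle; no pouch in the readable text |
| Readable label content (3.3.1) | Study number, kit number, storage and caution statements | The same |
| Steps in 6.4.2 | Partly redacted | No redaction shown; bottle leaves the carton before the first drop |

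The readable label content names no drug in either arm, so the labels do what labels can do. What remains different is the form of the container and how it is opened. The second-drop step for Proparacaine refers to a vial, but Section 3.3, Figure 2 and the neighbouring steps all call it a bottle. I read that as a wording slip.

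**2. Other safeguards.** No readable passage says that the containers match, that the kit is opened out of sight, or that the container is covered during instillation.

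**3. Does redaction explain the gap?** Only in part. Text is blacked out in the AG-920 description, the packaging section, the AG-920 dosing steps and SAP Section 2.4, and none of it can be counted as missing. But the sentence in Section 3.2 that names the masking measure is complete, and so is the Proparacaine sequence in 6.4.2. Hidden AG-920 steps cannot supply a shielding step for Proparacaine.

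**4. Is the family likely to be near?** Inclusion criterion 4 requires that the parent or guardian can be present at visits. Section 6.4.2 has them reminded about stinging just before the kit is retrieved. The documents do not say where the kit is opened or who watches.

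**5. Which outcomes are exposed?**
- Primary endpoint: judged by the investigator (Protocol Section 7; SAP Section 2.6), who is outside the mask under Section 3.5. Any effect of the family's mask is at most indirect, through the child's or parent's behavior.
- Adverse events: taken from the family at the call (6.4.4), counted as treatment-emergent through that call (8.3), with severity that may rest on the subject's report (8.3.2.3), and compared between arms by Fisher's exact test (9.4.8).

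**6. Size.** The Summary plans about 30 evaluable children per arm.
- One additional child with a reported event: 1/30 = 3.3 percentage points.
- Assumption for illustration: a true rate of 10% in both arms, and over-reporting in one arm of 0 to 10 points. Expected counts run from 30 × 0.10 = 3 v 3 to 30 × 0.20 = 6 v 3.
- Fisher's two-sided p for 6/30 v 3/30: with 9 events in all, only the 4/5 and 5/4 splits are more probable than the one observed, so p = 1 − 2 × C(30,4) × C(30,5) / C(60,9) = 1 − 2 × 0.264 = 0.47.

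Even at the upper end, the result is a distorted descriptive rate and not a false significant test.

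**The case against.** The strongest reply is that different containers do not by themselves reveal the assignment. This is a single-dose, parallel-group trial. Each family sees at most one container, has nothing to compare it with, and would need to know which container goes with which drug. Both cartons carry the same kind of study label. The consent pages are not available, so what families are told about the products cannot be seen. The appearance of the vial is also redacted. This stands, and it rules out three readings that a reader might infer:
- that the mask cannot hold;
- that up to all families would be unmasked;
- that many parents would recognise a clinic dropper bottle.

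The first two need facts the documents do not give, and no passage supports the third.

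A second reply is that little depends on it. The primary endpoint rests on an unmasked assessor. Both arms get the same warning about stinging. The investigator assigns causality and severity. SAP Section 2.9.3 limits treatment-emergent events to onset before the next day, and the SAP's adverse event text repeats no between-arm test. Most of this stands and keeps the point modest. It does not remove it: an event that began on Day 1 can still be reported at the call, and Protocol Section 9.4.8 still specifies the test.

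A third reply is that shielding may already exist in redacted text or site training. That is possible. Section 3.2, which is legible, nevertheless presents the label as the means of masking, and the legible Proparacaine steps contain no shielding.

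**Conclusion.** The concern holds in a limited form: the claim that families are masked throughout is not secured by the one measure the readable protocol names. The containers are visibly different, and at least in the Proparacaine arm the written procedure exposes the container without a step to conceal it.

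The proportion of families who would be unmasked is unknown. The direction and amount of any reporting bias are assumptions, and the 6 v 3 count is only an illustration. The exposure is mainly in family-reported adverse events and tolerability.

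Two further inferences should be resisted. Repairing the family mask would not protect the primary endpoint, because the investigator who judges it knows the treatment. Nor is the family mask the only masking language in the protocol: Section 9.3 refers to a masked evaluation for per-protocol membership, and Section 9.4.5 to deviations identified before unmasking. It is, however, the only masking of treatment during conduct that Section 3.5 and SAP Section 2.4 describe.

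This is a low-cost improvement and not a fatal flaw.

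**What to change.** Add to Protocol Sections 3.2 and 6.4.2, for both arms, that whoever doses the child (study staff in the Protocol; SAP Section 2.2 names the investigator) will:
- open the kit and ready the container out of the family's sight;
- instil the drops with the container covered by the hand or by an identical opaque sleeve;
- not name the product;
- return the container to the closed carton straight after dosing.

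The parent need not be kept away from the child. If such steps already exist in redacted text or training material, Section 3.2 should say so.

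The cost is a few sentences, brief site training, optional sleeves and slightly more awkward handling. Dose, timing, sample size and analysis are unchanged.

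If this is not adopted, remove the word throughout from Section 3.2 and report family-reported adverse events as potentially unmasked.
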